### **Cohort 1b2: Melanoma**

8.01) Patients with histologically- or cytologically-confirmed unresectable stage III or stage IV cutaneous melanoma not amenable to local therapy

8.02) Must have received at least one anti-PD(L1) therapy (including but not limited to nivolumab, pembrolizumab, atezolizumab, durvalumab, and avelumab) in the advanced or metastatic setting. Prior cytokine therapy (eg, IL-2, IFN- $\alpha$ ) and anti-CTLA-4 therapy (eg, ipilimumab) is also allowed.

8.03) Patients with BRAF mutations must have received prior BRAF inhibitor therapy (eg vemurafenib and dabrafenib) in the advanced or metastatic setting.

9.01) Inclusion Criteria for Additional Phase 1b Cohorts are included in [Appendix 11](#).

### 5.3 Exclusion Criteria

Patients are excluded from the study if any of the following criteria apply:

#### Medical Conditions

- 1.01) Decreased cardiac function with New York Heart Association (NYHA) > Class 2
- 1.02) Uncontrolled or significant heart disorder such as unstable angina
- 1.03) Current unresolved infection or history of chronic, active, clinically significant infection (viral, bacterial, fungal, or other) which, in the opinion of the investigator, would preclude the patient from exposure to a biologic agent or pose a risk to patient safety
- 1.04) Any uncontrolled medical condition or psychiatric disorder which, in the opinion of the investigator, would pose a risk to patient safety or interfere with study participation or interpretation of individual patient results
- 1.05) Active autoimmune disease, history of clinically significant autoimmune disease, or suspected autoimmune disease. Patients with type I diabetes mellitus, hypothyroidism requiring only hormone replacement, skin disorders (such as vitiligo, psoriasis, or alopecia) not requiring systemic treatment, or conditions not expected to recur in the absence of an external trigger, are permitted to enroll
- 1.06) Symptomatic interstitial lung disease or inflammatory pneumonitis
- 1.07) Untreated or active CNS or leptomeningeal metastases. Patients are eligible if metastases have been treated and patients are neurologically returned to baseline or neurologically stable (except for residual signs or symptoms related to the CNS treatment) for at least 2 weeks prior to the first dose of study treatment
- 1.08) Evidence of coagulopathy or bleeding diathesis

#### Prior/Concomitant Therapy

- 2.01) Treatment with any anti-cancer therapy or participation in another investigational drug or biologics trial within 28 days or  $\leq$  5 half-lives (whichever is shorter) prior to first dose of study treatment administration or while on this study
- 2.02) For patients participating in Phase 1a dose escalation and exploration cohorts: Prior treatment with a CTLA-4 antagonist, including ipilimumab and tremelimumab

2.03) Patients who have received prior immune-modulating therapies (including regimens containing an immune agonist or a PD-L1/PD-1 antagonist) are NOT permitted to enroll unless all the following apply:

- a. Must not have experienced a drug-related toxicity that led to permanent discontinuation of prior immunotherapy
- b. Last treatment was administered 5 half-lives or 90 days (whichever is shorter) prior to first dose of study treatment

2.04) Ongoing adverse effects from prior treatment > National Cancer Institute Common Terminology Criteria for Adverse Events (NCI CTCAE) Grade 1 (with the exception of Grade 2 alopecia or peripheral neuropathy)

### **Other Exclusions**

3.01) Immunosuppressive doses of systemic medications, such as steroids or absorbed topical steroids (doses > 10 mg/day prednisone or equivalent daily) must be discontinued at least 2 weeks before study treatment administration

3.02) QTcF > 450 msec for males or > 470 msec for females at screening

3.03) Severe allergic, anaphylactic, or other infusion-related reaction to a previous biologic agent

3.04) Known history of sensitivity to infusions containing Tween 20 (polysorbate 20), L histidine, and sucrose

3.05) Vaccines (eg, human papillomavirus [HPV] vaccine) within 4 weeks of study treatment administration. The inactivated seasonal influenza vaccine can be given to patients before treatment and while on therapy without restriction. Influenza vaccines containing live virus or other clinically indicated vaccinations for infectious diseases (eg, pneumovax, varicella) may be permitted, but must be discussed with the Sponsor's medical monitor and may require a study treatment washout period prior to and after administration of vaccine

3.06) Patients with abnormal serum chemistry values that in the opinion of the investigator are considered to be clinically significant. This will include patients who show clinical signs and symptoms related to their abnormal serum chemistry values as well as patients whose serum chemistry values are asymptomatic but clinically significant per investigator (eg, hypokalemia or hyponatremia).

3.07) Pregnant or breastfeeding

3.08) Known history of testing positive for human immunodeficiency virus (HIV) 1 or 2 or known acquired immunodeficiency syndrome (AIDS)

- 3.09) Positive test for hepatitis B virus surface antigen (HBsAg) or detectable hepatitis C virus ribonucleic acid (HCV RNA) indicating acute or chronic infection
- 3.10) Transfusion of blood or platelets or granulocyte-colony stimulating factor (G-CSF) administration completed within 72 hours prior to first dose of study treatment

No waivers of these inclusion or exclusion criteria will be granted.

#### **5.4 Lifestyle Considerations**

There is not enough information currently available to make any specific recommendations.

#### **5.5 Screen Failures**

Screen failures are defined as patients who consent to participate in the clinical study and enter the screening period but are not subsequently enrolled. A minimal set of screen failure information is required to ensure transparent reporting of screen failure patients to meet the Consolidated Standards of Reporting Trials (CONSORT) publishing requirements and to respond to queries from regulatory authorities. Minimal information includes demography, screen failure details, eligibility criteria, and any SAE.

Individuals who do not meet the criteria for participation in this study (screen failure) may be rescreened after discussion with the Sponsor. Patients who screen fail may repeat screening procedures one time, within the 28-day screening window, inclusive of informed consent. A patient who is rescreened is not required to sign another ICF if the rescreening occurs within the 28-day screening window.

## 6.0 STUDY INTERVENTION

Study intervention is defined as any investigational intervention(s), marketed product(s), placebo, or medical device(s) intended to be administered to a study patient according to the study protocol. For patients enrolled for evaluation of FPT155 monotherapy, the study intervention administered is FPT155. For patients enrolled for evaluation of combination treatment, the study interventions administered are FPT155 and pembrolizumab.

### 6.1 FPT155 Identity

FPT155 drug product is supplied for IV administration as a sterile, aqueous, colorless to slightly yellow, pyrogen-free solution supplied in single-use glass vials. The composition of the drug product contains 10 mg/mL active ingredient, 20 mM L-histidine, 270 mM sucrose, 0.05% (w/v) polysorbate 20 at pH 6.7. The drug product is provided in two configurations consisting of 20 mg/vial or 140 mg/vial. The container-closure systems consist of either an ISO 2R Type I glass vial, sealed with a 13 mm bromobutyl rubber stopper, and an orange flip-off cap containing a nominal volume of 2 mL or an ISO 20R Type I glass vial, sealed with a 20 mm bromobutyl rubber stopper, and a white flip-off cap containing a nominal volume of 14 mL. The final drug product will be provided as 2°C to 8°C refrigerated liquid which is diluted for administration per instructions provided in a separate Pharmacy Manual.

FPT155 will be supplied in a sterile vial for dilution into an IV container for administration by the study center.

### 6.2 Pembrolizumab Identity

Pembrolizumab for injection is a sterile, preservative-free, clear to slightly opalescent, colorless to slightly yellow solution that requires dilution for intravenous infusion. Each vial contains 100 mg of pembrolizumab in 4 mL solution. Each 1 mL solution contains 25 mg of pembrolizumab and is formulated in: L-histidine (1.55 mg), polysorbate 80 (0.2 mg), sucrose (70 mg) and Water for Injection. For additional information, refer to the local Keytruda® (pembrolizumab) Prescribing Information. FPT155 + pembrolizumab combination cohorts will enroll in Australia and South Korea.

Pembrolizumab is available for injection as a 50 mg lyophilized powder in single-use vial for reconstitution and in 100 mg/4 mL (25 mg/mL) solution in single use vial.

The injection is a sterile, preservative-free, clear to slightly opalescent, colorless to slightly yellow solution that requires dilution for intravenous infusion. Each 1 mL of solution contains 25 mg of pembrolizumab and is formulated in: L-histidine (1.55 mg), polysorbate 80 (0.2 mg), sucrose (70 mg) and water for Injection. Please refer to local pembrolizumab package insert.

## 6.3 Handling, Storage, and Accountability

### 6.3.1 FPT155

1. FPT155 should be stored under refrigerated temperature of 2-8°C. Shaking and long-term exposure to light should be avoided.
2. The investigator or designee must confirm appropriate temperature conditions have been maintained during transit for all study treatment received and any discrepancies are reported and resolved before use of the study treatment.
3. Only patients enrolled in the study may receive study treatment and only authorized site staff may supply or administer study treatment. All study treatments must be stored in a secure, environmentally controlled, and monitored (manual or automated) area in accordance with the labeled storage conditions with access limited to the investigator and authorized site staff.
4. The investigator, institution, or the head of the medical institution (where applicable) is responsible for study treatment accountability, reconciliation, and record maintenance (ie, receipt, reconciliation, and final disposition records).
5. The Investigator is responsible for returning all unused study treatment to the Sponsor (or designee) and must verify that no remaining supplies are in the Investigator's possession. The study site is permitted to destroy used or partially used study treatment vials according to the site policy once Sponsor approval of their documented destruction procedure has been obtained. On completion of the study, the number of FPT155 vials shipped, destroyed, and returned must be reconciled.
6. Further guidance and information for the final disposition of unused study treatment are provided in the pharmacy manual.

### 6.3.2 Pembrolizumab

For the combination cohorts pembrolizumab packaging, labelling, and storage of pembrolizumab should be in accordance with the local [Keytruda® package insert](#), the Pharmacy Manual, and relevant local guidelines.

## 6.4 Administration

### 6.4.1 FPT155

FPT155 will be administered as a 60 minute IV infusion Q3W in 21-day cycles. Proposed dose levels to be studied are outlined in Section 4.1.1.2.

There is no pre-specified maximum number of doses of FPT155.

A pharmacist (or other responsible person) will prepare FPT155 for administration. Doses in different cohorts should be prepared and administered according to the instructions provided in the Pharmacy Manual.

Infusion of FPT155 must be stopped, reduced, interrupted, or discontinued according to Section 6.9.3 (Dose Modification and Delay Criteria) and Section 6.9.6 (Dose Interruptions During Study Treatment Administration). If a patient experiences an infusion reaction, the patient's vital signs (temperature, blood pressure, pulse, and respiration rate) should be monitored during the infusion as well as every 30 minutes after the infusion for a minimum of 2 hours and until resolution of the infusion reaction.

### 6.4.2 Pembrolizumab

Pembrolizumab should be prepared and administered according to the pembrolizumab Product Information.

## 6.5 Method of Treatment Assignment

An Interactive Voice/Web Response System (IVRS/IWRS) will be used to assign patients to study treatment.

Patients in Phase 1a dose escalation will be sequentially assigned to dose levels at the time of enrollment, as described in Section 4.1.1.2. Patients in Phase 1a dose exploration will be assigned to the dose level and schedule selected based on the results of the Phase 1a dose escalation, as described in Section 4.2. Patients in Phase 1b dose expansion will be assigned to the dose level and schedule selected based on the results of Phase 1a, as described in Section 4.3.

## 6.6 Measures to Minimize Bias: Randomization and Blinding

This is an open label study. There is no randomization or blinding.

## 6.7 Study Intervention Compliance

Only qualified study center personnel may administer FPT155 or pembrolizumab. Pharmacy personnel trained in the study requirements will monitor compliance with the treatment assignments. Records of study medication administered (date, time, and dose administered

relative to time of preparation) will be recorded on the patient's electronic case report form (eCRF).

## 6.8 Concomitant Therapy

Any medication or vaccine (including over-the-counter or prescription medicines, vitamins, and/or herbal supplements) that the patient is receiving at the time of enrollment or receives during the study must be recorded along with:

- Reason for use
- Dates of administration including start and end dates
- Dosage information including dose and frequency

The medical monitor should be contacted if there are any questions regarding concomitant or prior therapy.

### 6.8.1 Permitted Concomitant Medications

Supportive care (e.g., antiemetics, analgesics, bisphosphonates, and RANK-L inhibitors) may be used at the investigator's discretion and in accordance with institutional procedures. Patients should receive antiemetic and other prophylactic treatments according to the local standard of care and manufacturer's instruction. Patients should receive full supportive care, transfusions of blood and blood products, antibiotics, antiemetics, etc., when appropriate. Hematopoietic stimulating agents may be used if indicated. Short course of focal radiation for palliation of symptoms is allowed. Patients are permitted to use topical, ocular, intra-articular, intranasal, and inhaled corticosteroids (with minimal systemic absorption). Adrenal replacement steroid doses > 10 mg daily prednisone are permitted. A brief (approximately less than 3 weeks) course of corticosteroids for prophylaxis (e.g., contrast dye allergy) or for treatment of non-autoimmune conditions (e.g., delayed-type hypersensitivity reaction caused by a contact allergen) and for the treatment of tumor-related AEs is permitted.

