#### Type of Patient and Disease Characteristics

- 2.01) Histologically confirmed solid tumors (except primary CNS tumors). For patients enrolled for treatment with FPT155+pembrolizumab: histologically confirmed non-small cell lung cancer not eligible for curative therapy.
- 2.02) For patients in Phase 1a dose escalation (all) and Phase 1a dose exploration (FPT155 monotherapy) only: Disease that is unresectable, locally advanced, or metastatic and has progressed following all standard treatments or is not appropriate for standard treatments.
- 2.03) All patients must have at least one measurable lesion at baseline according to RECIST v1.1. Tumor sites situated in a previously irradiated area, or in an area subjected to other loco-regional therapy, are not considered measurable unless there has been demonstrated progression in the lesion.
- 2.04) Availability of archival tumor tissue and consent to provide archival tumor for retrospective biomarker analysis, or consent to undergo a fresh tumor biopsy during screening
- 2.05) For patients participating in Phase 1a dose exploration cohorts and Phase 1b dose expansion: consent to undergo a mandatory fresh tumor biopsy during screening and on treatment
- 2.06) ECOG performance status of 0 or 1
- 2.07) Life expectancy of at least 3 months in the opinion of the investigator
- 2.08) Willing and able to comply with all study procedures
- 2.09) Prior radiotherapy must be completed at least 2 weeks before first dose of study treatment administration. No radiopharmaceuticals (eg, strontium, samarium) within 8 weeks before first dose of study treatment administration
- 2.10) Prior surgery that requires general anesthesia must be completed at least 14 days before first dose of study treatment administration unless patients have recovered, and it is considered safe after discussion with medical monitor. Surgery requiring local/epidural

anesthesia must be completed at least 72 hours before first dose of study treatment administration and patients must have recovered.

2.11) Screening laboratory values must meet the following criteria:

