### 6.8.2 Prohibited Concomitant Medications

Concomitant anticancer therapies of any kind including extensive non-palliative radiation are not permitted. Immunosuppressive doses of systemic corticosteroids are prohibited (unless utilized to treat a drug-related AE).

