6.1.7 Prior Anticancer Therapy

Number of prior regimens, time since the completion of last regimen will be summarized by treatment group using descriptive statistics. The best response to the last regimen will be summarized using summary statistics for a categorical variable. The summaries will be based on the Safety population as part of the disease-specific baseline characteristics.

The anti-cancer treatment, anti-cancer radiotherapy, anti-cancer surgery and procedures will be provided separately in a by-subject listing for Safety Population.

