6.2.1 Efficacy Endpoint: ORR

Objective Response Rate (ORR) is defined as the total number of patients with confirmed responses of either complete response (CR) or partial response (PR), as determined by the investigator per RECIST v1.1, divided by the total number of patients who are evaluable for a response. The best overall response (BOR) is the best response documented from first dose until the end of study, first disease progression, death, or start of new anti-cancer therapy, whichever is earlier. Subjects, who do not have sufficient baseline or on-study tumor status information to be adequately assessed for response status (i.e., those with BOR of not evaluable [NE]), or received anticancer therapy other than the study treatment, will be considered as non-responders and will be included in the denominators in calculations of response rates.

For the confirmed BOR, the algorithm below should be followed. The hierarchy of the categories for confirmed BOR is in the order listed.

- Confirmed CR: Check if the longest consecutive duration of CR (allow NE in between; duration starts at CR and ends at CR) is ≥ 4 weeks, if yes, set BOR to CR; otherwise:
- Confirmed PR: Check if the longest consecutive duration of PR (allow NE or CR in between; duration starts at PR and ends at PR/CR) is ≥ 4 weeks, if yes, set BOR to PR; otherwise:
- SD: Check if the best time-point response is CR or PR or SD, if yes, set BOR to SD; otherwise:

- PD: Check if the best time-point response is PD, set confirmed BOR to PD.
- NE: Otherwise set to NE.

Estimate of ORR and corresponding 2-sided exact 90% CI using the Clopper-Pearson method will be provided by treatment and overall. The Clopper-Pearson exact 90% CIs will be from SAS FREQ procedures with option BINOMIAL (EXACT). Patients who don't have any postbaseline adequate tumor assessments will be counted as non-responders.

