6.2.3 Efficacy Endpoint: DOR

Duration of Response (DOR) is defined as the time from first response (CR or PR determined by the investigator per RECIST v1.1) that is subsequently confirmed until the onset of progressive disease or death from any cause, whichever comes first.

DOR in months will be calculated as: (date of first progression or death from any cause – date of first confirmed CR or PR + 1)/30.4375. Patients who are alive and progression-free at the time of data analysis will be censored at the time of their last assessment for tumor response. DOR for CR and PR patients will be summarized using 25th, 50th (median), and 75th percentiles with associated 2-sided 90% CIs, as well as percentage of censored observations. The median will be estimated by using the Kaplan-Meier method and corresponding 2-sided 90% CI using Brookmeyer and Crowley methodology (using log-log transformation). The detailed censoring rules are displayed in [Table 10](#).

Table 10 Censoring Rules for DOR

Situation	Outcome	Date of Progression or Censoring	Event Description/ Censoring Reason
No baseline tumor assessments	Censored	Date of first dose	No baseline tumor assessment
No baseline tumor assessment, but death within two consecutive tumor assessments period after first dose	Censored	First tumor assessment date	No baseline tumor assessment
No post-baseline tumor assessments and no death	Censored	Date of first dose	No post-baseline tumor assessment

No post-baseline tumor assessment and death after two or more consecutive missing tumor assessments from first dose	Censored	Date of first dose	No post-baseline tumor assessment
Disease progression before receiving subsequent anticancer therapy or data cutoff, whichever happens first	Event	Date of first documented progression per RECIST v1.1 (excludes clinical progression)	PD
Death without documented PD and not receiving new anticancer therapy on or before data cutoff	Event	Date of death	Death
Disease progression or death after two or more consecutive missing tumor assessments	Censored	Date of last evaluable tumor assessment prior to disease progression or death	Two or more consecutive missing tumor assessments
Subsequent anticancer therapy received without documented PD or death prior or on the same day	Censored	Date of last evaluable tumor assessment prior to the date of initiation of subsequent anticancer therapy	Started new anti-myeloma treatment before PD or death.

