6.2.4 Efficacy Endpoint: PFS

Progression Free Survival (PFS) defined as time from the first dose of study treatment until the first documentation by the investigator of disease progression per RECIST v1.1 or death from any cause, whichever comes first.

PFS in months will be calculated as: (date of first progression or death from any cause - date of first dose + 1)/30.4375. Patients who are alive and progression-free at the time of data analysis will be censored at the time of their last assessment for tumor response. PFS will be summarized using 25th, 50th (median), and 75th percentiles with associated 2-sided 90% CIs, as well as percentage of censored observations. The median will be estimated by using the Kaplan-Meier method and corresponding 2-sided 90% CI using Brookmeyer and Crowley methodology (using log-log transformation). The same censoring rules as DOR will be applied. See details in [Table 10](#).

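### Palliative radiation may be given to a RECIST target lesion, and no rule keeps the resulting shrinkage out of the response assessment

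*Protocol*

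**What the plan says.** Protocol 6.8.1 lists palliative radiation among permitted supportive measures: "Short course of focal radiation for palliation of symptoms is allowed". It sets no limit on site and does not mention target lesions. Protocol 6.8.2 adds: "Concomitant anticancer therapies of any kind including extensive non-palliative radiation are not permitted".

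Inclusion criterion 2.03 (Protocol 5.1) says that sites in a previously irradiated area "are not considered measurable unless there has been demonstrated progression in the lesion". That rule decides what is measurable at baseline. Protocol 8.1.1 and 8.1.2 cover scan timing, method and investigator assessment, and say nothing about a lesion irradiated after baseline. By contrast, Protocol 8.6.2 does keep biopsies away from target lesions.

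In SAP 6.2.1, best overall response is "the best response documented from first dose until the end of study, first disease progression, death, or start of new anti-cancer therapy", whichever comes first, and patients who "received anticancer therapy other than the study treatment, will be considered as non-responders". SAP Table 10 (in 6.2.3) has a censoring row headed "Subsequent anticancer therapy received without documented PD or death prior or on the same day", and SAP 6.2.4 says of PFS: "The same censoring rules as DOR will be applied". None of these places mentions palliative radiation or defines anticancer therapy. SAP 6.1.7 does name radiotherapy ("The anti-cancer treatment, anti-cancer radiotherapy, anti-cancer surgery and procedures will be provided separately in a by-subject listing for Safety Population"), but that section concerns prior therapy.

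**The concern.** RECIST response rests on the sum of target-lesion diameters. If one of those lesions is irradiated for symptoms, the sum falls for a reason other than FPT155. Criterion 2.03 requires only one measurable lesion, so the irradiated lesion may be the whole sum.

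At stake are ORR, DOR and PFS (and, in narrower circumstances, DCR) in Phase 1b, and ORR in the pembrolizumab combination part. All are read by the investigator with no control arm, so nothing in the design cancels the error. The primary safety endpoints are not affected.

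There is a second, smaller risk. The non-responder clause in SAP 6.2.1 carries no time limit. A programmer who took palliative radiation to be anticancer therapy could recode a genuine responder who was irradiated at a painful non-target site.

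**Working it through.** **Step 1. Which rule could catch an irradiated target lesion?**
- Criterion 2.03, and section 3.1.3 of RECIST 1.1 (Protocol Appendix 6), apply to measurability at baseline only.
- Protocol 8.1.1 and 8.1.2 contain no rule.
- The best-response algorithm in SAP 6.2.1 works on time-point responses and takes the sum as given.
- SAP Table 10 acts only on anticancer therapy, missing assessments, progression and death.
- The RECIST 1.1 questions-and-answers appendix gives case-by-case advice for a target lesion that becomes non-evaluable. Its example is a change of technique and it refers to a review panel, which neither document sets up for response.

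No rule removes the shrinkage.

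**Step 2. What it does to the sum.** Change = (new sum − reference) / reference. The lesion sizes are illustrative assumptions.
- False response: one target lesion, 30 mm irradiated to 20 mm. (20 − 30)/30 = −33.3%, which meets the 30% decrease for PR.
- Masked progression: lesions of 40 and 30 mm, both growing 25%. Without radiation the sum is 50 + 37.5 = 87.5 mm against 70 mm, +25.0% and +17.5 mm, which is PD. If the 40 mm lesion is irradiated to 20 mm, the sum is 20 + 37.5 = 57.5 mm, −17.9%, which is read as SD.

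**Step 3. The plan's own figures.** Clopper-Pearson 90% limits are the 5% quantile of Beta(x, n − x + 1) and the 95% quantile of Beta(x + 1, n − x). For n = 25 and x = 5 to 10 these give 8.2–37.5, 11.0–42.0, 13.9–46.2, 17.0–50.4, 20.2–54.4 and 23.6–58.3%. This reproduces Protocol Table 10 and the statement in Protocol 9.2 that an observed 24% excludes 10%.

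**Step 4. One false response at the boundary.**

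| Responses | ORR | Exact 90% CI | Excludes 10%? |
|---|---|---|---|
| 5/25 | 20.0% | 8.2–37.5% | no |
| 6/25 | 24.0% | 11.0–42.0% | yes |
| 6/30 | 20.0% | 9.1–35.7% | no |
| 7/30 | 23.3% | 11.5–39.4% | yes |

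The n = 30 rows matter because Protocol 9.4.1 puts the main efficacy analysis on all treated patients. One response is worth 1/25 = 4.0 points or 1/30 = 3.3 points.

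**Step 5. Sensitivity, by assumption.** The documents give no radiation rate. Suppose a fraction f of true non-responders is called a response. At a true ORR of 10% the apparent rate is 0.10 + 0.90f. The probability of at least 6/25 is then 3.3% (f = 0), 4.8% (1%), 6.6% (2%), 14.4% (5%) or 33.5% (10%).

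**Step 6. DCR.** SAP 6.2.1 sets best response to SD if the best time-point response is SD, PR or CR, with no minimum duration. A patient already stable at one scan therefore counts whatever happens later, and a false PR in a stable patient changes nothing. DCR rises essentially only when radiation comes before any stable scan and hides PD.

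**The case against.** The case against has four parts.

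- **The endpoints carry no formal decision.** The synopsis calls this an estimation trial without a clinical hypothesis, and Protocol 9.1 marks hypotheses as not applicable. This stands, and it limits the weight of the point.
- **It will be uncommon.** A false PR also needs no new lesion, no non-target progression and confirmation at 4 weeks or more. Bone lesions without a measurable soft-tissue component cannot be target lesions. This stands too, but the frequency is unknown in both directions.
- **Any single response error crosses the 10% line at this size.** That is true. This error, however, has a known direction and a rule can prevent it.
- **The protocol already classifies palliation.** A reader might infer that the plan is equally open to the opposite bias, with palliative radiation counted as anticancer therapy and responders lost. The documents do not support that as an even choice. Protocol 6.8.1 expressly permits palliation, while 6.8.2 bans anticancer therapy of every kind and, for radiation, names only the extensive non-palliative sort. Something permitted cannot sit in a wholly banned class. What remains is a missing cross-reference in the SAP. This reading also leaves the irradiated target lesion untouched.

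A reader might also infer that the protocol ignored the request in RECIST 1.1 section 3.1.3 to say when irradiated lesions are measurable. It did not: that passage concerns baseline, and criterion 2.03 answers it.

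**Conclusion.** The point holds for target lesions irradiated on study. Followed as written, the plan can score radiation shrinkage as PR or let it hide PD. ORR is biased upward and DOR and PFS are lengthened; the effect on DCR is confined to the timing in Step 6. The SAP's silence on whether permitted palliation is anticancer therapy is a lesser fault that invites misuse of the untimed non-responder clause.

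The size per event is 4.0 points of ORR at n = 25 or 3.3 at n = 30, enough to decide the 10% benchmark when a cohort sits at the boundary. The expected size cannot be given, because it depends on a radiation rate that neither document states; Step 5 is a range of assumptions. A reader might infer that the error would trigger a wrong go decision, but no go/no-go rule on ORR is stated. It is worth correcting because these single-arm, investigator-read estimates need one reproducible rule and the rule is cheap.

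**What to change.** 1. **Protocol 6.8.1.** Before documented PD, direct palliative radiation to non-target lesions where clinically possible, without withholding palliation that a patient needs. Record the irradiated site and date.
2. **SAP 6.2.1.** From the date a target lesion is irradiated, later time points are not evaluable (NE) for CR, PR and SD unless standard RECIST 1.1 PD is met: the sum of all target lesions, unequivocal non-target progression, or a new lesion. Responses confirmed before radiation stand.
3. **SAP 6.2.1 and SAP Table 10.** State that permitted palliative radiation is not anticancer therapy for these rules. State also that the NE scans in item 2 are not missing assessments, since otherwise a later PD could be censored under the row for two or more consecutive missing assessments.

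Declaring PD from the non-irradiated lesions alone, or from regrowth of the irradiated one, may look attractive but departs from RECIST 1.1. With 20 + 30 = 50 mm after radiation, regrowth from 20 to 26 mm gives 56 mm (+12%), and growth from 30 to 37.5 mm gives 57.5 mm (+15%). Neither reaches the 20% increase in the whole sum.

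The cost is a sentence in 6.8.1, a short SAP rule and a site-and-date field; SAP 6.3 already tabulates concomitant procedures. A few time points become non-evaluable, and a PR not yet confirmed at the time of radiation could not be confirmed afterwards. The lengthening of DOR and PFS is reduced, not removed, because PD on the whole sum may still be reached late. Radiation to a non-target site can also still hide non-target progression.
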